4.5. Sponsor Qualified Medical Personnel

The contact information for the sponsor's appropriately qualified medical personnel for the trial is documented in the study contact list located in the study manual and Study Team on Demand (SToD) system'.

To facilitate access to appropriately qualified medical personnel on study related medical questions or problems, subjects are provided with a contact card. The contact card contains, at a minimum, protocol and investigational compound identifiers, patient study number, contact information for the investigational site and contact details for a help desk in the event that the investigational site staff cannot be reached to provide advice on a medical question or problem originating from another healthcare professional not involved in the subjects participation in the study. The help desk number can also be used by investigational staff if they are seeking advice on medical questions or problems, however it should only be used in the event that the established communication pathways between the investigational site and the study team are not available. It is therefore intended to augment, but not replace the established communication pathways between the investigational site and study team for advice on medical questions or problems that may arise during the study. The help desk number is not intended for use by the subject directly and if a subject calls that number they will be directed back to the investigational site.

5. STUDY TREATMENTS

5.1. Allocation to Treatment

Subjects will be assigned a single subject identification number which will be obtained at the time of screening using the Interactive Voice Response System (IVRS)/Interactive Web Response System (IWR) and retained throughout the study. A separate randomization number will be assigned to subjects who meet the inclusion/exclusion criteria by the IVRS/IWR at randomization and will be recorded on the case report form (CRF). Subjects will be centrally randomized to receive 1 of 2 treatment arms (ziprasidone or placebo) in a 1:1 ratio according to a computer generated pseudo-randomization code using the method of permuted blocks.

5.2. Breaking the Blind

The study will be subject, investigator, and sponsor blinded.

At the initiation of the study, the study site will be instructed on the method for breaking the blind. The method will be an electronic process utilizing the IVR/IWR system. Blinding codes should only be broken in emergency situations for reasons of subject safety. Whenever possible, the investigator or sub-investigator consults with a member of the study team prior to breaking the blind. When the blinding code is broken, the reason must be fully documented and entered on the case report form.

5.3. Drug Supplies

5.3.1. Formulation and Packaging

Study medication will be provided by Pfizer and will include oral ziprasidone capsules of 20 mg, 40 mg, 60 mg, and 80 mg strength or matching placebo capsules. All medication will be packaged in child resistant blister cards with columns for AM and PM capsules.

Two different types/designs of blister cards will be provided over the course of the study: a titration card design and a fixed dose card design. Each card will contain medication for 7 days plus 3 additional days. All child resistant blister cards will have 1 capsule available for the AM and 1 capsule for the PM administration of each day. Each AM or PM column will contain either a 20 mg, 40 mg, 60 mg or 80 mg ziprasidone capsule (or matching placebo).

Titration cards will be provided for the first week of treatment for subjects weighing ≥ 45 kg and those weighing <45 kg. Subjects weighing ≥ 45 kg will also receive a second titration card at Day 8/Visit 3 for the second week of treatment. Subjects weighing <45 kg will not receive a titration card at Day 8/Visit 3; instead they will receive a fixed dosing card which will allow them either to continue on their current dose or to change to a higher or lower dose, depending on the clinical judgment of the investigator.

Titration Card Container Types	
Active or Placebo (separate cards for Day 1/Visit 2 and Day 8/Visit 3)	≥45 kg body weight
Active or Placebo (for Day 1/Visit 2 only)	<45 kg body weight

In order to accommodate the flexible dosing permitted by the protocol, 7 types of fixed dosing cards, each with a different total daily dose of study drug, will be provided as illustrated below for both active and placebo capsules:

Fixed Dose Card Container Types		
Total Daily Dose	AM Dose	PM Dose
40 mg	20 mg	20 mg
60 mg	20 mg	40 mg
80 mg	40 mg	40 mg
100 mg	40 mg	60 mg
120 mg	60 mg	60 mg
140 mg	60 mg	80 mg
160 mg	80 mg	80 mg

5.3.2. Preparation and Dispensing

Study medication will first be dispensed at the baseline visit (Day 1) after all baseline assessments have been completed. Treatment assignments will be made in accordance with the randomization sequence. Every blister card supplied to the site will have a unique number. The site will select a weight-based dosing regimen within the IVR/IWR system, and the IVR/IWR system will assign a container number that contains the indicated regimen. The weight-based dosing regimen selected at the start of the trial will continue to be applied throughout the trial; weight fluctuations of the subjects will not be considered to reassign a subject to a different weight based dosing group (ie, ≥45 kg body weight or <45 kg body weight).

At each subsequent medication dispensing visit (Day 8/Visit 3, Day 15/Visit 4, and Day 22/Visit 5), subjects will be assigned one blister card for the following study week. The IVR/IWR system will cap the total daily dosage allowed so subjects cannot be prescribed a dose higher than the maximum dose allowed per protocol (ie, subjects <45 kg cannot exceed 80 mg total daily dose and subjects ≥45 kg cannot exceed 160 mg total daily dose). The system will also not allow fixed dosing cards to be dispensed when there is an incremental jump of more than 20 mg/day compared to the last fixed dosing card dispensed (ie, a 120 mg/day fixed dose card could not be dispensed if the last fixed dose card dispensed

was an 80 mg/day card). The only exception to this rule is for subjects ≥ 45 kg where an increase from 120 mg/day to 160 mg/day will be allowed on Day 14 of the study. In addition, the IVR/IWR system will not allow more than one blister card at a time to be issued to a subject.

On Day 1 (Baseline Visit), a single titration card will be dispensed based on the subject's weight (subject ≥ 45 kg or < 45 kg) for the first week of dosing (see Table 1 and Table 2 below). The titration cards that will be used for the first week of the trial will have a maximum of 80 mg/day for subjects ≥ 45 kg and a maximum of 60 mg/day for subjects < 45 kg.

Table 1. ≥ 45 kg Titration Regimen for Day 1/Visit 2

Day	AM Dose (mg)	PM Dose (mg)	Total Daily Dose (mg)
1	-	20	20
2	20	20	40
3	20	20	40
4	20	40	60
5	20	40	60
6	40	40	80
7	40	40	80
8	40	40	80
9	40	40	80
10	40	40	80

Table 2. < 45 kg Titration Regimen for Day 1/Visit 2

Day	AM Dose (mg)	PM Dose (mg)	Total Daily Dose (mg)
1	-	20	20
2	20	20	40
3	20	20	40
4	20	20	40
5	20	40	60
6	20	40	60
7	20	40	60
8	20	40	60
9	20	40	60
10	20	40	60

At Day 8/Visit 3, subjects weighing ≥ 45 kg would typically receive a second titration card (see [Table 3](#) below) which will increase their total daily dose to 120 mg/day (reached on Day 10 of the study).

Table 3. ≥45 kg Titration Regimen for Day 8/Visit 3

Day	AM Dose (mg)	PM Dose (mg)	Total Daily Dose (mg)
1	40	60	100
2	40	60	100
3	60	60	120
4	60	60	120
5	60	60	120
6	60	60	120
7	60	60	120
8	60	60	120
9	60	60	120
10	60	60	120

However, the investigator can also choose to provide a fixed dose card with a different daily dose, eg, 100 mg/day or 80 mg/day (see Table 4 and [Table 5](#) below), if in his or her clinical judgment that is the more appropriate choice.

Table 4. 100 mg Fixed Dose Regimen

Day	AM Dose (mg)	PM Dose (mg)	Total Daily Dose (mg)
1	40	60	100
2	40	60	100
3	40	60	100
4	40	60	100
5	40	60	100
6	40	60	100
7	40	60	100
8	40	60	100
9	40	60	100
10	40	60	100

Table 5. 80 mg Fixed Dose Regimen

Day	AM Dose (mg)	PM Dose (mg)	Total Daily Dose (mg)
1	40	40	80
2	40	40	80
3	40	40	80
4	40	40	80
5	40	40	80
6	40	40	80
7	40	40	80
8	40	40	80
9	40	40	80
10	40	40	80

Subjects weighing ≥ 45 kg should be provided the 160 mg/day fixed dose card (see Table 6) only if they have tolerated 120 mg/day; in addition, the 160 mg/day fixed dose card should not be issued before Day 14 of the study.

Table 6. 160 mg Fixed Dose Regimen

Day	AM Dose (mg)	PM Dose (mg)	Total Daily Dose (mg)
1	80	80	160
2	80	80	160
3	80	80	160
4	80	80	160
5	80	80	160
6	80	80	160
7	80	80	160
8	80	80	160
9	80	80	160
10	80	80	160

At Day 8/Visit 3, subjects weighing <45 kg can either be maintained on their Day 7 dose (see [Table 7](#)) or the dose can be increased to 80 mg/day (see Table 5) or decreased to 40 mg/day (see [Table 8](#)). The investigator will decide which fixed dose blister card to provide to the subject for the following week, based on clinical judgment.

Table 7. 60 mg Fixed Dose Regimen

Day	AM Dose (mg)	PM Dose (mg)	Total Daily Dose (mg)
1	20	40	60
2	20	40	60
3	20	40	60
4	20	40	60
5	20	40	60
6	20	40	60
7	20	40	60
8	20	40	60
9	20	40	60
10	20	40	60

Table 8. 40 mg Fixed Dose Regimen

Day	AM Dose (mg)	PM Dose (mg)	Total Daily Dose (mg)
1	20	20	40
2	20	20	40
3	20	20	40
4	20	20	40
5	20	20	40
6	20	20	40
7	20	20	40
8	20	20	40
9	20	20	40
10	20	20	40

Only site personnel according to their role as determined on the site delegation log may dispense study medication cards. Subjects will be instructed to take one capsule in the AM and one capsule in the PM from each assigned blister card.

Subjects are not allowed to leave the clinic with more than one blister card in their possession.

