1.2.2.1. Background on Previous Ziprasidone Pediatric Trials

1.2.2.1.1. Study A1281123: Open Label Safety & Tolerability

Study A1281123 was an open-label safety and tolerability study in children and adolescents 10-17 years old, diagnosed with Bipolar I (manic or mixed), schizophrenia or schizoaffective disorder. This Phase 2 study explored the range of tolerated doses of ziprasidone during 3-weeks of low or high fixed dose administration, and characterized the safety and tolerability of flexibly dosed ziprasidone for an additional 24 weeks. Ziprasidone oral suspension was titrated over 10 days to a target dose following a fixed schedule, and then maintained at the target dose until end of Week 3 (Period 1). Two dose ranges were tested: Group 1 subjects (low dose, n=23) started from 10 mg BID to a target dose of 40 mg BID, and Group 2 subjects (high dose, n=40) started from 20 mg BID to a target dose of 80 mg BID. Doses for subjects weighing <45 kg were halved. Subjects could continue flexible dosing in a range of 10-80 mg BID into Period 2 for up to 24 additional weeks. The most common AEs in Groups 1 and 2 were sedation (21.7%, 35.0%), somnolence (34.8%, 27.5%), nausea (21.7%, 27.5%), headache (13.0%, 27.5%), dizziness (13.0%, 25.0%), and vomiting (13.0%, 20%). No unexpected safety or tolerability findings occurred. ECG findings were consistent with those recorded for adult subjects treated with ziprasidone. There were no confirmed QTc intervals over 500 msec and no subject had a QTc increase \geq 60 msec from baseline. Most subjects (89%) continued treatment in the 6-month open-label flexible dose extension; and 31 (55%) completed the 6-month treatment. Only sedation (30.4%) and somnolence (30.4%) occurred in more than 20% of the subjects. Weight gain was reported as an adverse event (AE) in 5 of 56 subjects (8.9%). No clinically relevant changes in lipid profile or fasting glucose were observed. Twenty SAEs were reported in 16 subjects. One event (QTc prolongation) was initially reported as related to treatment; this event occurred after termination of therapy, and the causality was subsequently changed to not related to study drug. All other events were unrelated to treatment. Five cases of suicidal ideation and one of self-harm (overdose) were explained by the underlying disorder, pre-existing suicidal ideation, and situational stressors. The higher AE rate in Group 2 (high dose group) in the A1281123 study was attributed partly to the relatively high initial dosing (20 mg BID) and partly to the relatively fast, fixed titration to 80 mg BID, which may not have been tolerated well by some subjects. On the basis of these results, a lower starting dose and a slower, flexible dose titration schedule with lower target dose range were identified for the placebo-controlled Phase 3 studies in pediatric subjects.

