5.3.3. Administration

As study drug administration is complex, the parent or guardian should closely supervise dosing throughout the study, especially during the titration period. One capsule is taken in the morning and one capsule in the evening about 12 hours apart. If a dose is missed, the missed dose should be taken as soon as possible, but the AM and PM doses should be separated by a minimum of 4 hours.

All study medication is to be taken with food. Capsules are to be taken intact. Swallow the capsule whole. Do not crush or chew the capsule.

In general, the target dose should be attained by Days 7-14. For subjects with a body weight ≥ 45 kg, the target dose range is 120-160 mg/day. A dose of 160 mg/day should not be achieved before Day 14 of treatment.

For subjects with a body weight < 45 kg, the target dose range is 60-80 mg/day. A dose of 80 mg/day should not be achieved before Day 8 of treatment.

5.3.3.1. Baseline (Day 1)/Visit 2

At the baseline visit, after all baseline assessments have been completed, each randomized subject will receive one titration blister card for the first week of treatment, which will be assigned based on the subject's body weight (< 45 kg or ≥ 45 kg). The body weight used to determine this assignment will continue to be applied throughout the trial; weight fluctuations of the subject will not be considered to reassign a subject to a different weight based dosing group. The investigator or a staff member will explain the titration card to each subject and his/her parent or guardian, and clearly specify that one capsule must be taken from the AM column with food and one capsule from the PM column with food, sequentially from each row (day) until the next study visit. (See [Table 1](#) and [Table 2](#) for the Day 1/Visit 2 titration blister cards). All subjects will take the first dose of study medication (20 mg or placebo) from the Day 1 row (PM column) in the afternoon or evening of the baseline visit. There will be no AM dose of study medication for Day 1. The subject's first AM dose will be on Day 2.

After the baseline visit, the investigator or designated staff must be in contact with the subject and/or his/her parent(s) and/or guardian(s) at least once during the week, either by telephone or in person, to ensure that the subject is taking the proper capsules at the proper time and to monitor the tolerability, safety, and efficacy of the study drug.

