5.3.3.2. Day 8/Visit 3 (end of Week 1)

At Day 8/Visit 3, the investigator should review the clinical response of each subject and determine whether to continue the current study drug dose or to increase or decrease it.

Subjects weighing ≥ 45 kg should be issued the Day 8/Visit 3 titration card (see [Table 3](#)). However, the investigator can also choose to provide a fixed dose card with a different daily dose, eg, 100 mg/day or 80 mg/day (see tables [Table 4](#) and [Table 5](#)), if in his or her clinical judgment that is the more appropriate choice.

Subjects weighing <45 kg should be issued a fixed dosing card with the desired total daily dose for the second week of double-blind therapy (ie, either 40 mg/day, 60 mg/day, or 80 mg/day; see [Table 5](#), [Table 7](#), or [Table 8](#)).

A dose of 160 mg/day for subjects with a body weight ≥ 45 kg should not be achieved before Day 14 of treatment, and a dose of 80 mg for subjects with a body weight <45 kg should not be achieved before Day 8 of treatment.

Following the Day 8/Visit 3 clinic visit, the investigator or designated staff must be in contact with the subject and/or his/her parent(s) and/or guardian(s) at least once during the week, either by telephone or in person, to ensure that the subject is taking the proper capsules at the proper time and to monitor the tolerability, safety, and efficacy of the study drug.

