5.3.3.5. Day 29/Visit 6 (end of Week 4)

At the Day 29/Visit 6 (end of Week 4) clinic visit, the investigator should review the clinical response of each subject and obtain the end of treatment assessments (see [Section 6.4](#)). The Day 29/Visit 6/end of Week 4 visit must be scheduled in the morning hours. Subjects should be instructed to come to the visit fasting, before taking their morning study medication dose, since subjects will be required to take their morning medication under supervision at the site.

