6. STUDY PROCEDURES

The subject and the legal representative must understand the nature of the study and be able to comply with protocol requirements. The investigator, or a person designated by the investigator, will obtain written informed consent from each subject's legal representative and a written assent from the subject before any trial specific activity is performed. Subjects who turn 18 years old during the study need to give a written consent unless State law states otherwise, and such State law shall apply.

The subject should be assigned a subject number from the IVR/IWR system after obtaining informed consent. AEs must be recorded from the time that the informed consent is signed.

Every effort should be made to bring the subject back to the office on the designated study days; however, office visits will have a ± 3 day visit window to allow for slight variations in subject schedules unless approved on an individual subject basis by the sponsor. When scheduling subsequent visits, the overall treatment period in the protocol should be maintained.

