7.2.5. Blood Pressure/Pulse (Sitting and Standing)

Blood pressure (mm Hg) should be measured using a manual aneroid or mercury sphygmomanometer with a cuff appropriate to the subject's arm girth placed over the bare skin. Subjects should rest sitting with feet flat on the floor at least 5 minutes before sitting blood pressure readings are taken. The sitting pulse rate (beats/minute) should be measured after the blood pressure. Pulse rate should be measured for at least 30 seconds.

After standing for approximately 2 minutes, another blood pressure reading will be taken followed by a standing pulse reading.

Whenever possible, the subject should refrain from products containing nicotine or caffeine 2 hours before taking blood pressure measurements. Also, whenever possible, blood pressure measurements should be taken on the same arm throughout the study.

Blood pressure and pulse will be measured according to the [Schedule of Activities](#). At Visit 6/Week 4, subjects will take their morning study medication during the visit. Blood pressure and pulse will be measured before study medication dosing (trough).

7.2.6. 12-lead Electrocardiogram (ECG)

A 12-lead ECG will be conducted at various time points according to the [Schedule of Activities](#).

Readings and interpretations of ECG tracings will be performed centrally. Information to be reported by the central scoring site will include the subject's demographic information; beats per minute (bpm); overall interpretation; rhythm type; respiratory rate; heart rate intervals PR, QRS, QT, QTcF (ms), and QTcB (ms); and any comments. The values of QTcF will be used for clinical decision making and interpretative assessment of changes in QTc. QTcB will be measured to enable comparisons with historical data but not used for clinical decisions due to inaccuracies of the Bazett's formula in correcting for heart rate.

All ECGs must be obtained before or at least 3 hours after food intake. ECGs must be obtained **prior to blood pressure/pulse measurements and prior to collection of any blood sample** CCI because these assessments can affect the ECG. To standardize the collection procedure, the ECG should be collected in a comfortable and quiet place after the subject has been allowed to rest in a supine position for approximately 5 minutes.

Baseline and Visit 6 (end of treatment/early termination) ECGs must be administered in triplicate, tracings should be collected approximately 2 minutes apart.

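### For subjects ≥45 kg, an early in-window Visit 3 can take the calendar-day dose from 60 to 100 mg/day with no full day at 80; a Day 7 gate would close this minor gap

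*Protocol*

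**What the plan says.** All of this concerns subjects weighing at least 45 kg.

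- **First card (Protocol Section 5.3.2, Table 1).** 60 mg/day (20 AM + 40 PM) on Days 4 and 5; 80 mg/day (40 + 40) from Day 6. Section 5.3.3.1 has subjects take the capsules "sequentially from each row (day) until the next study visit".
- **Second card (Table 3).** 100 mg/day (40 + 60) in rows 1 and 2, then 120 mg/day (60 + 60). Section 5.3.2 says that this card will "increase their total daily dose to 120 mg/day (reached on Day 10 of the study". It is the default: under Section 5.3.3.2 these subjects "should be issued the Day 8/Visit 3 titration card". The investigator first reviews response and may instead give a fixed card, with 100 and 80 mg/day named as examples.
- **Window (Section 6 and the Schedule of Activities).** Sites are asked to make every effort to keep the designated days, but there is a ±3 "day visit window to allow for slight variations in subject schedules". Visit 3, nominally Day 8, may therefore fall on Days 5 to 11.
- **System check (Section 5.3.2).** "The system will also not allow fixed dosing cards to be dispensed when there is an incremental jump of more than 20 mg/day", measured against the last fixed card. The one named exception is 120 to 160 mg/day on Day 14.
- **Date limits (Section 5.3.3).** 160 mg/day is not to be reached before Day 14, nor 80 mg/day before Day 8 in subjects under 45 kg. No date limit is given for 100 mg/day in the heavier group.

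**The concern.** A site that follows the default inside the permitted window can give a child 60 mg one day and 100 mg the next, with no full day at 80 mg/day between. On the nominal Day 8 schedule no step exceeds 20 mg/day. The jump check compares fixed cards with fixed cards, so as worded it covers neither a switch from one titration card to another nor a first fixed card at Visit 3.

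The stake is tolerability. Section 1.2.2.1.1 attributes the higher adverse event rate in the high-dose group of study A1281123 partly to the high starting dose and partly to a "relatively fast, fixed titration to 80 mg BID, which may not have been tolerated well by some subjects", and says that a slower titration was chosen for Phase 3 as a result. At a Day 5 or 6 visit, the Visit 3 ECG and tolerability review also come before a full day at 80 mg/day.

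**Working it through.** **Which card supplies the visit-day capsules?** The protocol does not say for Visit 3. Only Visit 6 (Section 5.3.3.5) asks subjects to attend "before taking their morning study medication dose". Section 7.2.6 says "All ECGs must be obtained before or at least 3 hours after food intake", and drug is taken with food, so Visit 3 can come before or after the morning capsule. Three readings were tried against the plan's own figure, 120 mg/day on Day 10 after a Day 8 visit:

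- A: both visit-day capsules come from Table 3. Row 3 falls on Day 8 + 2 = Day 10. Fits.
- B: the AM capsule comes from the first card and the PM capsule from Table 3 row 1; row 2 is the next day. Row 3 again falls on Day 10. Fits.
- C: Table 3 starts the day after the visit. Row 3 falls on Day 11. Does not fit, so it is not relied on.

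**Daily totals (mg), overlaying Table 3 on Table 1:**

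| Visit 3 | Reading | Days 1–8 | Largest step | Days totalling 80 | First day at 120 |
|---|---|---|---|---|---|
| Day 5 | A | 20, 40, 40, 60, 100, 100, 120, 120 | 40 | 0 | 7 |
| Day 5 | B | 20, 40, 40, 60, 80, 100, 120, 120 | 20 | 1 | 7 |
| Day 6 | A and B | 20, 40, 40, 60, 60, 100, 100, 120 | 40 | 0 | 8 |
| Day 7 | A and B | 20, 40, 40, 60, 60, 80, 100, 100 | 20 | 1 | 9 |
| Day 8 | A and B | 20, 40, 40, 60, 60, 80, 80, 100 | 20 | 2 | 10 |

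On Day 6 the reading makes no difference, because the AM capsule is 40 mg on both cards: 20 + 40 = 60 on Day 5, then 40 + 60 = 100 on Day 6. On Day 5 it does: A gives 40 + 60 = 100, B gives 20 + 60 = 80. For visits on Days 9–11 the largest step is also 20.

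**100 mg fixed card.** Its first row is also 40 + 60, so it makes the same step. No fixed card has been dispensed before Visit 3, so the stated check has nothing to compare it with.

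**Capsule by capsule (Day 6 visit).** Day 5 is 20, 40 and Day 6 is 40, 60. Sums of successive pairs are 20 + 40 = 60, 40 + 40 = 80 and 40 + 60 = 100. The Day 5 visit under A gives the same 60, 80, 100. Over a rolling 24 hours the dose does pass through 80 mg.

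**Comparison with study A1281132 (Section 1.2.2.1.2).** It started at 20 mg/day and rose by 20 mg/day every 1 or 2 days. At daily increases that is 20, 40, 60, 80, 100, 120, 120, 120 on Days 1–8. No sequence in the table is higher on any day; only the size of one step is larger.

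**The case against.** The strongest reply is that the 40 mg step comes from counting by calendar day. Each capsule rises by only 20 mg, and the rolling 24-hour total goes 60, 80, 100. That stands, although the protocol itself titrates and sets its limits in mg/day.

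Three stronger readings may tempt a reader, and the documents support none of them.

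- *The protocol breaks its own 20 mg/day limit.* No general maximum step is stated. The check is confined to fixed cards, and the protocol accepts a 40 mg/day step from 120 to 160, for subjects who have tolerated 120. Reaching 120 mg/day on Day 7 or 8 is also within the Day 7–14 range for attaining the target.
- *The step recreates the tolerability problem of A1281123.* That study's high-dose group started at 20 mg BID and was titrated on a fixed schedule to 80 mg BID over 10 days. Here subjects start at 20 mg/day, the default cards stop at 120 mg/day, and the dose never exceeds the fastest pace of A1281132, which the protocol describes as generally well tolerated.
- *The Week 4 efficacy result is affected.* Nothing in the documents suggests so.

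Existing safeguards also count: sites aim for the designated day, contacts are required before and after Visit 3, the dose may be lowered at any time, and the investigator may give the 80 mg fixed card. That last option removes the step, but no text points to it for an early visit. It also caps the next fixed card at 100 mg/day, while Section 5.3.3.3 provides only for continuing or lowering the dose at Visit 4, so the subject could stay below target. Finally, the full IVR/IWR specification is not in the documents, and an unstated date check may exist.

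**Conclusion.** The gap is real and minor. A Day 6 visit allows a 60 to 100 mg/day calendar-day step under both card-switch readings that fit the plan's Day 10 figure; a Day 5 visit allows it under one of the two. From Day 7 on, no step exceeds 20 mg/day. This rests on the default Table 3 card or the 100 mg fixed card being issued at the early visit, and on the IVR/IWR doing only what Section 5.3.2 describes. How often Visit 3 would fall on Day 5 or 6 is not given, so the number of subjects affected cannot be estimated. It is worth correcting because the remedy is nearly free and matches date gates the protocol already uses elsewhere, not because a dose limit is breached or harm is shown.

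**What to change.** For subjects weighing at least 45 kg, do one of the following.

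1. **Preferred:** set the Visit 3 window to Days 7–11 (−1/+3), with a footnote to the Schedule of Activities and a sentence in Section 5.3.3.2. The largest step is then 20 mg/day. Row 3 of Table 3 falls two days after the visit, so 120 mg/day is reached on Days 9–13, inside the Day 7–14 range.
2. **Alternative:** have the IVR/IWR refuse any card opening at 100 mg/day (Table 3 or the 100 mg fixed card) before Day 7. A subject seen on Day 5 or 6 stays on the first card through Day 6 and receives Table 3 afterwards. Started on Day 7, this gives 60, 80, 100, 100, 120 on Days 5–9.

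The first option costs a little scheduling freedom at one visit. The second costs one date check, plus an extra in-person contact for an early attender, since only site staff may dispense cards and a telephone call would not do.
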